7.8.2 Laboratory data

The analyses of laboratory data will be descriptive in nature and will be based on BI standards (5). The same on-treatment period as considered for the analysis of AEs will be applied for laboratory values. CTC grade for applicable lab parameters will be calculated according to CTCAE v3.0 (7).

For a list of laboratory parameters considered for this trial, please refer to CTP Section 5.2.3, Table 5.2.3:1. Descriptive statistics of all normalized laboratory values by visit will be provided including changes from baseline. Transition tables of CTCAE grade from baseline to worst value and last value on treatment, and frequency tables of possible clinically significant abnormalities will be produced. For those parameters that have CTC grading possible clinically significant abnormalities are defined as those laboratory values with a CTC grade ≥ 2 that have had an increase of ≥ 1 grade from baseline. For those parameters for which no CTC grade has been defined standard BI project definitions will be used to decide on clinical significance. See [Tables 7.8.2: 1](#) and [7.8.2: 2](#) for the potential clinical significance rules.

Analyses of descriptive statistics will use normalized lab values (variables ULN, LABN). Analyses of frequencies of patients with potential clinical significance, analyses of shift, and liver function categories tables will use converted values (ULC, LABSTD).

Summaries will be produced of laboratory data recorded on-treatment. Listings will be provided for data recorded prior to treatment, on-treatment and post-treatment. For details on the treatment definition, see [Section 6.1](#).

For the primary laboratory parameters listed in Table 7.8.2: 1, full analysis of descriptive statistics, transition tables and possible clinically significant abnormalities will be conducted.

Analysis of secondary laboratory parameters listed in [Table 7.8.2: 2](#) will be limited to frequency tables of possible clinically significant abnormalities. Listings of converted and normalized values for all laboratory parameters considered for this trial will be provided in Appendix 16.2 of the CTR.

Table 7.8.2: 1 Primary laboratory parameters

Label	Lab test name	Direction of interest	Potential clinical significance rule
ALKP	Alkaline phosphatase	High	A ¹
APTT	APTT (Activated partial thrombopl. time)	High	A ¹
CRE	Creatinine	High	A ¹
CRECL	GFR/Creatinine clearance	Low	A ^{1,2}
HGB	Haemoglobin	Low	A ¹
INR	PT-INR	High	A ¹
K	Potassium	Low	A ¹
LYMPH	Lymphocytes	Low	A ¹
NA	Sodium	Low	A ¹
NEUT	Neutrophils	Low	A ¹
SGOT	AST/GOT, SGOT	High	A ¹
SGPT	ALT/GPT, SGPT	High	A ¹
TBILI	Bilirubin, total	High	A ¹
WBC	White blood cell ct.	Low	A ¹

¹A = CTCAE grade 2 or greater with an increase of at least one CTCAE grade from baseline.

²Values less than 0.25xLLN will be assigned CTCAE grade 3.

Table 7.8.2: 2 Secondary laboratory parameters

Label	Lab test name	Direction of interest	Potential clinical significance rule
BUN	Blood urea nitrogen	High	> 10
CA	Calcium	Low & High	A ¹
CK	Creatine kinase	High	A ¹
GLUB	Glucose	Low & High	A ¹
LDH	LDH	High	≥ 3xULN
TPRO	Protein, total	Low & High	< 45, > 100
UREA	Urea	High	> 1.5xULN
URIC	Uric acid	High	A ^{1,3}

¹A = CTCAE grade 2 or greater with an increase of at least one CTCAE grade from baseline.

³Values >ULN – 10 mg/dL or ≤0.59 mmol/L will be assigned CTCAE grade 1.

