7.3.3 Safety analyses

DLTs will be tabulated for each dose cohort in the Phase I dose finding part. The tabulation will be done in two ways: (1) DLTs with onset in the first treatment course; (2) all DLTs regardless of treatment course at onset. The definition of DLT is defined in [Table 4.1.4.1:2](#).

Events that started within the course of treatment, starting after the first administration of the treatment and until 28 days after the last administration of treatment will be considered as having occurred on treatment. In general later events will be attributed to the post-study period and will be presented separately. However post-study events will be examined to determine whether they need to be combined with on-treatment events in an additional table.

Adverse events will be graded according to CTCAE v3.0 and reported according to BI standards. Serious adverse events will be tabulated. In addition, events leading to dose reduction or treatment discontinuation will be examined, but may not be reported as individual tables, depending upon the extent of overlap.

Descriptive statistics will be used to describe changes in laboratory parameters over time. In addition, all abnormalities of potential clinical significance will be reported. In general, potential clinical significance is defined as at least CTCAE Grade 2 and an increase in

Proprietary confidential information.

© 2017 Boehringer Ingelheim International GmbH or one or more of its affiliated companies. All rights reserved.

This document may not - in full or in part - be passed on, reproduced, published or otherwise used without prior written permission.

CTCAE classification from baseline. The incidence and intensity of adverse events will be correlated descriptively with pharmacokinetic data if possible.

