
6. Medullo-blastomas and PNETs
	
see HGG
 
Many patients already demonstrate symptoms of systemic metastases at diagnosis and clinical may be dominated by symptoms of metastases (loss of function, pain);
 
Histopathology Homer Wright rosettes or at least two of the below mentioned markers must be present: translocation t(11;22)(q24;q12) (1), t(21;22)(q22;q12) or t(7;22)(p22;q12); NSE, S100 synaptosin, chromogranin, vimentin, cytokeratin, actin und LCA stains are performed
 
Usually patients show elevated levels of LDH and ferritin in their blood labs;
 
Imaging exams include but are not limited to Xray, Ct, MRI and ultrasound; in case of metastatic disease FDG-PET is used.
 
Tumour biopsies are mandated to confirm the initial diagnosis.
	
surgery, radiation and chemotherapy; combination chemotherapy for medulloblastoma: vincristine, carbo-/cisplatin, cyclophosphamide and/or lomustine, etoposide, TMZ; Chemotherapy for PNETs, like those for neuroblastoma: combinations of agents like alkylating agents (ifosfamide, cyclophosphamide), anthracyclines(adriamycin), etoposide, actinomycin D and vincristine

7. RMS
	
Clinical symptoms largely depend on the location of the tumour
 
Imaging exams include but are not limited to Xray, CT, MRI and ultrasound; in case of metastatic disease FDG-PET is used.
 
Tumour biopsies are mandated to confirm the initial diagnosis, and should be performed as open surgical intervention to assure that sufficient material is obtained for histopathology, IHC and cyto-, and molecular genetical exams. Myogenin, MyoD1, desmin, vimentin, myoglobin, actin, NSE, S-100, MIC2 stains are done. Furthermore e.g. in alveolar RMS - t(2;13)(q35;q14)) exams are done.
	
Treatment options for high- risk limited; conventional treatment with chemotherapy, surgery and radiotherapy; chemotherapy: dactinomycin, vincristine, alkylating agents (ifosfamide, cyclophosphamide), anthracyclines (doxorubicin and epidoxorubicin), etoposide, and platinum compounds.

Proprietary confidential information.

© 2017 Boehringer Ingelheim International GmbH or one or more of its affiliated companies. All rights reserved.

This document may not - in full or in part - be passed on, reproduced, published or otherwise used without prior written permission.

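### The SAP's significance limits for LDH, BUN, urea and total protein have no baseline condition, so the on-treatment frequency tables mix newly worsened values with values already abnormal at entry

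*SAP*

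**What the plan says.** SAP 7.8.2 sets two kinds of rule for a possibly clinically significant laboratory abnormality. For parameters with CTC grading it counts "laboratory values with a CTC grade ≥ 2 that have had an increase of ≥ 1 grade from baseline". For the rest, "For those parameters for which no CTC grade has been defined standard BI project definitions will be used to decide on clinical significance". It then sends the reader to Tables 7.8.2:1 and 7.8.2:2 for the rules.

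Every row of Table 7.8.2:1 (primary parameters) uses rule A, which footnote 1 defines as "CTCAE grade 2 or greater with an increase of at least one CTCAE grade from baseline". In Table 7.8.2:2 (secondary parameters), calcium, CK, glucose and uric acid use rule A. The other four rows do not carry that footnote:

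- LDH: at least 3xULN
- BUN: "Blood urea nitrogen High > 10"
- Urea: above 1.5xULN
- Total protein: below 45 or above 100

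Analysis of the secondary parameters "will be limited to frequency tables of possible clinically significant abnormalities". On the period covered, the section says "Summaries will be produced of laboratory data recorded on-treatment". Listings cover values before, during and after treatment.

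**The concern.** Within one set of tables, rule A rows count patients who got worse and the four ungraded rows count patients beyond a limit, whatever they had at entry. Because the output is labelled on-treatment, a reader will tend to take every row as treatment-emergent.

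LDH is where this is most likely to matter. Protocol Appendix 10.5 says of medulloblastoma/PNET: "Usually patients show elevated levels of LDH and ferritin in their blood labs". It also lists LDH among the neuroblastoma laboratory examinations. Both diagnoses were eligible for dose finding. Both can also enter the expansion part through the other-solid-tumour or exploratory cohorts. No exclusion criterion in Protocol 3.3.3 limits LDH. A value raised by the disease at entry can therefore persist on treatment and appear in the table as an on-treatment abnormality.

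**Working it through.** The plan states no figure on this point, so there is none to reproduce. The check has two steps.

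**Step 1: apply the printed rules to example patients.** LDH is in multiples of ULN. As written, a patient counts if the on-treatment value is at least 3. The comparison rule adds that the baseline must be below 3.

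| Baseline to on-treatment | As written | With baseline below limit required |
|---|---|---|
| 1.0 to 3.2 (new) | counted | counted |
| 3.5 to 3.5 (stable) | counted | not counted |
| 4.0 to 3.1 (improving) | counted | not counted |
| 3.5 to 1.5 (resolved) | not counted | not counted |
| 3.5 to 7.0 (worse) | counted | not counted |

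Under rule A, a CK that stays at Grade 2 throughout is not counted, because the grade did not rise. An LDH falling from 4.0 to 3.1xULN is counted. This is the inconsistency.

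The table shows two more things. A patient abnormal at baseline is counted only if an on-treatment value also meets the limit (row 4). Simply requiring a normal baseline would drop a genuine worsening from the count (row 5).

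**Step 2: scale.** Inputs from Protocol 7.6: up to 38 expansion patients and up to 55 in total (17 + 38). Let p be the share of patients beyond the limit both at baseline and on treatment. The documents give no value for p, so it is an assumption.

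- One such patient moves a row by 1/38 = 2.6 percentage points, or 1/55 = 1.8 points.
- Expected number = n x p. For n = 38: 38 x 0.05 = 1.9 and 38 x 0.15 = 5.7, so about 2 to 6. For n = 55: 55 x 0.05 = 2.75 and 55 x 0.15 = 8.25, so about 3 to 8.
- Chance of at least one = 1 - (1 - p)^n. For n = 38 this is 54% at p = 2%, 86% at 5% and 98% at 10%. For n = 55 it is 67%, 94% and above 99%.

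The counts include patients who stayed the same, improved or worsened while beyond the limit. What they share is that they did not newly cross it.

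**The case against.** The strongest objection is that SAP 7.8.2 rests on internal BI laboratory standards (SAP references 5 and 6), which are not available here. They may already say how to handle patients abnormal at baseline. That cannot be excluded. However, the SAP names its own two tables as the place where the rules are found, and they print no such condition for these four parameters.

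Several stronger readings are tempting but not supported:

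- *A conflict with the protocol.* Protocol 7.3.3 begins "In general, potential clinical significance is defined as at least CTCAE Grade 2 and an increase in" and is expressed in CTCAE classification. It is a general statement and cannot govern parameters that the SAP treats as having no CTC grade.
- *Tumour-related elevation in all four tests.* The documents support this for LDH only. The statement comes from a table of tumours considered for dose finding, and elevated does not mean 3xULN. For BUN, urea and total protein the issue is prior abnormality of any cause. Exclusion criterion 14 (renal function) makes a high baseline BUN or urea less likely.
- *Every patient abnormal at baseline inflates the row.* This is false. Row 4 of the table above is not counted.
- *The baseline cannot be recovered.* SAP 7.8.2 plans pre-treatment listings. One of its sentences also promises by-visit descriptive statistics with changes from baseline for all normalised values, although a later sentence limits secondary parameters to frequency tables. By-visit summaries would not show which counted patients were already beyond the limit.
- *The table overstates drug toxicity.* It is descriptive and makes no causal claim. Relatedness is assessed through adverse events.

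Flagging every value beyond a fixed limit is a defensible, cautious choice in a small first-in-child trial. That supports keeping such values visible. It does not support leaving them unseparated from new ones.

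**Conclusion.** The point holds as a minor reporting defect. Followed as printed, the rules for LDH, BUN, urea and total protein count patients who were beyond the limit before afatinib and remain so, even when improving, beside rows that count only worsening. This can overstate new abnormalities. Whether it will depends on how many patients enter beyond a limit and stay there, which the documents do not say. The range of about 2-6 of 38, or 3-8 of 55, rests entirely on the assumed 5-15%. It also rests on the SAP tables being the complete rule. DLT, MTD, OR and PFS are not touched.

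**What to change.** In SAP 7.8.2, for LDH, BUN, urea and total protein (low and high limits separately):

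1. Cross-tabulate baseline status (within limit, beyond limit, missing) against worst on-treatment status.
2. Headline the patients newly beyond the limit.
3. For patients already beyond it at baseline, show separately whether the worst on-treatment value was worse than baseline, so that a rise from 3.5 to 7.0xULN stays visible.
4. Add a footnote to Table 7.8.2:2 saying that these four rows are absolute limits. If the BI standards already contain a baseline rule, print it there.
5. Reconcile the sentence promising changes from baseline for all normalised values with the one limiting secondary parameters to frequency tables.

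For the programming, take baseline as defined in SAP 6.7. Table 6.1:1 starts the on-treatment period on the date of first intake, so a day 1 pre-dose sample assigned by date alone could otherwise enter the on-treatment side.

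The cost is one small extra table and a footnote. No new data are needed, because Protocol 5.2.3 already schedules these tests at screening and on day 1 of each course.

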Proprietary confidential information.

© 2017 Boehringer Ingelheim International GmbH or one or more of its affiliated companies. All rights reserved.

This document may not - in full or in part - be passed on, reproduced, published or otherwise used without prior written permission.

- 5 Before any trial procedure, both the patient and/or parent/legal guardian have to give informed consent/assent according to the local regulatory requirements. At each moment along the trial, the site staff must disclose and discuss any new information that might affect willingness to continue trial participation with the patient and/or parent/legal guardian. For the MTD expansion cohorts/phase II part a high rate of screening failures is expected. Therefore a [pre-screening](#) informed consent may be used to allow collection and testing of tumour tissue for ErbB deregulations (see section [3.3.2](#)). Upon confirmation of positivity for selection biomarkers and before to proceed with trial procedures the informed consent/assent for trial entry, as mentioned earlier in this footnote, must be signed.
 - 6 Pulmonary examination must include transdermal O₂ saturation at screening, at visit 1 of each course and EOT. It should be repeated as clinically indicated during the trial and may be supplemented by a chest X-ray if clinically indicated.
 - 7 Measurement of height (in cm) will be performed on day1 every other courses.
 - 8 Safety lab tests should not be repeated if previous tests are not older than 48 hours.
 - 9 Safety lab test at visits 2, 3, 4 of courses 1 and 2 to be limited as described in [Section 5.2.3](#).
 - 10 Mandatory for female patients of child bearing potential (post menarchal) within 7 days prior to first treatment and at EOT. To ensure early detection of pregnancy, test might be repeated as necessary during the treatment period depending on the local law.
 - 11 ECG is required at screening, at C1V2, V1 every third course thereafter (i.e. C4V1, C7V1...) and EOT.
 - 12 Left ventricular ejection fraction (LVEF) at screening, at end of course 1 (C2V1 visit) and to be repeated C4V1, every 3rd course thereafter (C7V1...) and EOT.

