3.3.3 Exclusion criteria

1. Chemotherapy within 3 weeks prior to the start of study treatment, biological therapy or investigational agents within 4 weeks prior to the start of study treatment or prior to passing 5 half-lives, i.e. systemic clearance, whatever comes first
2. Radiotherapy within 2 weeks before starting study treatment (palliative radiotherapy is allowed if not focused on a target lesion)
3. Surgery within 4 weeks before starting study treatment or planned surgery during the projected course of the study which compromises patient's trial participation by investigator judgement
4. Known hypersensitivity to afatinib or its excipients
5. History or presence of clinically relevant cardiovascular abnormalities as per investigator judgement
6. Female patients of childbearing potential, who are nursing or are pregnant
7. Any history of or concomitant condition that, in the opinion of the investigator, would compromise the patient's ability to comply with the study or interfere with the evaluation of the efficacy and safety of the test drug

Proprietary confidential information.

© 2017 Boehringer Ingelheim International GmbH or one or more of its affiliated companies. All rights reserved.

This document may not - in full or in part - be passed on, reproduced, published or otherwise used without prior written permission.

8. Requirement of treatment with a prohibited concomitant medication listed in the CTP that cannot be stopped for the duration of trial participation
9. Known pre-existing interstitial lung disease (ILD), or signs and symptoms indicative of the latter as per investigator judgement (see [Section 4.2.1](#))
10. Any history or presence of poorly controlled gastrointestinal disorders that could affect the intake/absorption of the study drug (e.g. Crohn's disease, ulcerative colitis, chronic diarrhoea, malabsorption) as per investigator judgement
11. Active hepatitis B infection (defined as presence of HepB sAg and/ or Hep B DNA), active hepatitis C infection (defined as presence of Hep C RNA) and/or known HIV carrier
12. Known keratitis
13. Inadequate liver function (AST/ALT>2.5xULN, Bilirubin>1.5xULN adjusted for age)
14. Inadequate kidney function, i.e. creatinine>1.5xULN adjusted for age and/or creatinine clearance <70 ml/min/1.73m² estimated by institutional standard formula for estimation of GFR in paediatric patients
15. Inadequate bone marrow function (ANC ≤1000/mm³, platelets ≤100000/mm³)

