If a patient experiences DLT (for definition refer to [Table 4.1.4.1:2](#)), therapy may be continued at a reduced dose (for dose reduction, refer to [Table 4.1.4.3:1](#)) after recovery of the respective adverse event(s) to pre-dose CTCAE grade(s). The investigator shall liaise with BI and ask for confirmation of the dose of the trial drug before a new treatment course is started for any patient. In questionable cases, the DMC might be involved in decision making. If a patient is not eligible for further therapy, the patient has to discontinue further treatment with the trial drug.

Proprietary confidential information.

© 2017 Boehringer Ingelheim International GmbH or one or more of its affiliated companies. All rights reserved.

This document may not - in full or in part - be passed on, reproduced, published or otherwise used without prior written permission.

Table 4.1.4.1:2 Dose limiting toxicities

Dose limiting toxicity (DLT)

DLTs are defined as any of the following events that are considered related to afatinib:

1. CTCAE grade 4 hematologic toxicity lasting for 7 days
 2. CTCAE Grade 3 or 4 non-hematologic toxicity (except fever grade 3).
 3. CTCAE Grade 2 or higher decrease in cardiac left ventricular function
 4. CTCAE Grade 2 or higher worsening of renal function as measured by serum creatinine, newly developed proteinuria, or newly developed decrease in glomerular filtration rate
 5. CTCAE Grade 2 diarrhoea persisting for 7 or more days, despite supportive treatment (loperamide treatment or other effective anti-diarrhoeal medication)
 6. CTCAE Grade 2 nausea and/or vomiting persisting for 7 or more days despite antiemetic treatment
 7. CTCAE grade 5 events
-

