5.2.3 Assessment of safety laboratory parameters

Safety laboratory samples will be analyzed at the investigator's local laboratory. Safety laboratory examinations will include hematology, biochemistry and urine examinations. Table 5.2.3: 1 presents the laboratory tests to be performed at screening, Day1 of each course and/or EOT whatever applies.

Table 5.2.3:1 Clinical Laboratory Tests

Category	Parameters
Haematology	Haemoglobin (Hb), platelet count, white blood cell count (WBC), with differential (neutrophils, lymphocytes, monocytes)
Coagulation	International Normalized Ratio (INR), activated Partial Thromboplastin Time (aPTT)
Chemistry	
Electrolytes	sodium, potassium, calcium, magnesium, chloride, bicarbonate (HCO ₃)
Liver function tests	alkaline phosphatase, aspartate aminotransferase (AST), alanine aminotransferase (ALT), γ -glutamyltransferase (GGT), total bilirubin
Renal function parameters	Blood urea/blood urea nitrogen (BUN), creatinine; Creatinine clearance estimate by institutional standard formula for estimation of GFR in paediatric patients.
Category	Parameters
Other	glucose, albumin, phosphorus, lactate dehydrogenase (LDH), total protein, uric acid, creatine phosphokinase (CK); in case of pathological CPK further evaluation (e.g by determination of isoenzymes, troponin assays, ECG exam) should be performed as clinically indicated, CRP
Urinalysis	pH, protein, glucose, erythrocytes, leucocytes, nitrite and, if clinically indicated ketones, urobilinogen, specific gravity; in case of pathological finding(s) further evaluation should be performed and results of the latter must be documented
Pregnancy test	β -HCG testing in urine or serum in girls of childbearing potential (WOCBP)

Proprietary confidential information.

© 2017 Boehringer Ingelheim International GmbH or one or more of its affiliated companies. All rights reserved.

This document may not - in full or in part - be passed on, reproduced, published or otherwise used without prior written permission.

Limited lab tests (Hb, WBC, ANC, thrombocytes) will be required at intermediary visits

The investigator should complete additional evaluations of laboratory tests as clinically indicated. Any abnormal findings from these investigations need to be reported as an Adverse Event. For confirmation of laboratory findings indicative for drug induced liver injury (DILI), local laboratories will be used

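### Platelets are in neither SAP laboratory table, so the plan gives them no laboratory-based CTCAE shift table and no count of Grade 2 or higher worsening

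*SAP*

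**What the plan says.** Protocol 5.2.3, Table 5.2.3:1, gives the haematology tests as "Haemoglobin (Hb), platelet count, white blood cell count (WBC), with differential (neutrophils, lymphocytes, monocytes"). The reduced panel is set out below that table: "Limited lab tests (Hb, WBC, ANC, thrombocytes) will be required at intermediary visits". Flow chart footnote 9 schedules it: "Safety lab test at visits 2, 3, 4 of courses 1 and 2 to be limited as described in" Section 5.2.3. Exclusion criterion 15 (Protocol 3.3.3) uses platelets as a threshold: "Inadequate bone marrow function (ANC ≤1000/mm³, platelets ≤100000/mm³").

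For analysis, Protocol 7.3.3 promises that "all abnormalities of potential clinical significance will be reported". In general this means CTCAE Grade 2 or above together with a rise in grade from baseline.

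SAP 7.8.2 refers to Protocol Table 5.2.3:1 for the parameters considered. It then allocates the outputs. The Table 7.8.2:1 parameters get everything: "For the primary laboratory parameters listed in Table 7.8.2: 1, full analysis of descriptive statistics, transition tables and possible clinically significant abnormalities". The analysis of the Table 7.8.2:2 parameters "will be limited to frequency tables of possible clinically significant abnormalities".

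**The concern.** A parameter that is in neither SAP table is assigned neither a transition table nor an abnormality count. For platelets this looks like an oversight. The other three interim counts are all primary parameters, SAP Section 4 gives no reason for treating platelets differently, and the SAP history table says the July 2020 revision updated the safety laboratory analysis.

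At stake is a count that does not depend on the investigator's view. Under Protocol 5.2.2.1 a laboratory change becomes an adverse event only if the investigator judges it clinically relevant. Haemoglobin, white cells and neutrophils are reported both through that filter and from graded laboratory values. Platelets would be reported, by grade, only through the filter.

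**Working it through.** No sample size, power or error rate is involved. The check is a row-by-row comparison of the protocol panel with the two SAP tables.

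**Step 1. Rows in the SAP tables.**
- Table 7.8.2:1: ALKP, APTT, CRE, CRECL, HGB, INR, K, LYMPH, NA, NEUT, SGOT, SGPT, TBILI, WBC = 14 rows.
- Table 7.8.2:2: BUN, CA, CK, GLUB, LDH, TPRO, UREA, URIC = 8 rows.
- 14 + 8 = 22 rows, none of them platelets.

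**Step 2. The four interim tests against the tables.**

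| Interim test | In Protocol Table 5.2.3:1 | In SAP Table 7.8.2:1 | Direction, rule | In SAP Table 7.8.2:2 |
|---|---|---|---|---|
| Haemoglobin | yes | yes (HGB) | Low, A | no |
| White cells | yes | yes (WBC) | Low, A | no |
| Neutrophils | yes | yes (NEUT) | Low, A | no |
| Platelets | yes | **no** | none given | **no** |

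Three of the four are primary parameters; 4 − 3 = 1 is missing.

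**Step 3. Is platelets a special case?** Nine blood parameters of Protocol Table 5.2.3:1 are in neither SAP table: platelets, monocytes, magnesium, chloride, bicarbonate, GGT, albumin, phosphorus and CRP. Of these nine, only platelets are also in the interim panel and in an eligibility criterion.

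**Step 4. What platelets receive under SAP 7.8.**

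| Output | Platelets covered? |
|---|---|
| By-visit descriptive statistics with change from baseline | Yes, by the general sentence covering all normalised values |
| Listings in Appendix 16.2 of the report | Yes |
| AE and DLT tables by highest CTC grade (SAP 7.8.1) | Yes, if a low count is reported as an AE |
| CTCAE transition table, baseline to worst and last value | Not assigned |
| Frequency of Grade 2 or higher with a rise from baseline | Not assigned |

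**Step 5. Against Protocol 7.3.3.** The protocol's general definition of potential clinical significance matches rule A in the SAP: Grade 2 or higher and at least one grade above baseline. The last row of Step 4 is therefore the output closest to what 7.3.3 describes, and it is one of the two that platelets lack.

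**The case against.** The best counter-argument is that the SAP never says unlisted parameters are excluded. Section 7.8.2 starts from the protocol's parameter table, says that transition and abnormality tables will be produced, and gives a generic rule for any CTC-graded parameter. The only limiting word applies to the secondary list. The section also rests on a company laboratory standard that is not available here. This has some force. But the general text names no parameters and sends the reader to the two tables for the significance rules, and the later sentences divide the outputs by table. On the generous reading, platelets still lack a stated direction of interest, and the same one-row change settles the matter.

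Four stronger conclusions that a reader might draw are not supported:

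- **That thrombocytopenia goes unsummarised.** The AE tables count it by grade when it is reported as an AE. A platelet DLT would also be an adverse event of special interest (Protocol 5.2.2.1) with its own tables. By-visit statistics and listings remain as well.
- **That the SAP flatly contradicts Protocol 7.3.3.** That section promises reporting, prescribes no shift or frequency table for each parameter, and qualifies its definition as general. Listings and AE tables are forms of reporting, though weaker ones than a count.
- **That DLT counting or the MTD is at risk.** DLT criterion 1, "CTCAE grade 4 hematologic toxicity lasting for 7 days", covers platelets only by class. DLTs are reported events considered related to afatinib and are not derived from the SAP laboratory tables. The dose-finding part is complete (Protocol 4.1.3).
- **That the other unlisted chemistry tests, such as magnesium, phosphorus, albumin and GGT, must be added.** Ranking parameters as primary, secondary or listing-only is a legitimate choice, and none of these tests is in the interim panel or the eligibility threshold cited above. Sodium, potassium, creatinine and GFR already get full analysis.

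The practical consequence is also tempered by Protocol 1.2, which describes a mainly gastrointestinal and dermatological adverse-event profile.

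On the other side, a sentence in Protocol 5.2.3 asks for abnormal findings to be reported as AEs. It follows directly on additional, clinically indicated tests, so it does not clearly remove the investigator filter for the scheduled panel.

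**Conclusion.** The point holds as a gap in one parameter's safety reporting. Platelets are absent from all 22 rows, while the other three of the four interim tests receive full analysis. Two outputs are missing: the laboratory-based CTCAE shift table and the count of Grade 2 or higher worsening. AE tables replace them only in part. Protocol 7.3.3 is incompletely met rather than contradicted. No primary or secondary endpoint changes, and neither does the MTD.

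This rests on three assumptions. First, the sentences allocating outputs by table govern the general ones before them. Second, the two tables are complete as read. A row lost in reading the PDF cannot be wholly excluded, but the rows run alphabetically, a label beginning with PL would sit between NEUT and SGOT, and no break or redaction is visible there. Third, the company laboratory standard does not add platelets by default.

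**What to change.** Add one row to SAP Table 7.8.2:1: platelets, direction of interest Low, potential clinical significance rule A. This assumes that platelets carry a CTCAE v3.0 grade, as the other counts under rule A do. If the omission was deliberate, SAP 7.8.2 should say so and give the reason.

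The cost is a one-row SAP revision and the matching output. Platelets are already measured with the full and the limited panels, so no new data, visits or protocol amendment are needed. No other row needs to change on this account.
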